5.6.2.2 AE summaries

The following AE summaries for participant incidence and event number will be provided by weight-categorized dose group for the Initial Treatment Period, OLE Period, and the combined periods. Selected summaries as noted will report exposure adjusted rates. An overall summary of the AEs will also be provided. AE tables will summarize Dose A (320mg, 160mg, Total), Dose B (all) and All Participants on one page; the subsequent page will contain Dose B (64mg, 32mg, Total), Dose A (all) and All Participants.

- Summary by system organ class (SOC), HLT, and preferred term (PT):
 - Any TEAE (with exposure-adjusted rates)
 - Serious TEAE (with exposure-adjusted rates)
 - TEAEs leading to withdrawal from the study (with exposure-adjusted rates)
 - TEAE leading to discontinuation of investigational medicinal product (IMP) (with exposure-adjusted rates)
 - TEAE leading to death
 - Related TEAE
 - Related serious TEAE
 - TEAE for safety topics of interest and safety topics closely monitored (with exposure-adjusted rates)
- Summary by relationship, SOC, HLT, and PT
 - Any TEAE
 - TEAE leading to death (for EudraCT reporting purposes)
- Summary by maximum relationship, SOC, HLT, and PT
 - Any TEAE
- Summary by severity, SOC, HLT, and PT
 - Any TEAE
- Summary by maximum severity, SOC, HLT, and PT
 - Any TEAE

Ordered and subset of AE summaries will be reported in a separate table to facilitate review when needed. Examples include:

- Serious TEAE by SOC and PT
- Nonserious TEAE by SOC and PT above reporting threshold of 5%

- Any TEAE by decreasing frequency of PT

The following summary will be provided for antibody data (Section 5.7.1.4.1.6 and Section 5.7.1.4.2.1):

- Incidence of TEAEs per 100 participant years by SOC, HLT, and PT and by time of onset relative to ADAb status. Note: Only presented for combined Initial Treatment Period and OLE Period.
- Incidence of TEAEs per 100 participant years by SOC, HLT, and PT and by time of onset relative to NAB status. Note: Only presented for combined Initial Treatment Period and OLE Period.

The following AEs will be listed separately:

- Any TEAE with onset at day 1
- Any TEAE related to TB including latent TB and IGRA tests

The following summaries will be produced for the Plain Language Summaries:

- Incidence of Drug-related TEAEs – Overview
- Incidence of Drug-related TEAEs by Preferred Term
- Incidence of Serious Drug-related TEAEs by Preferred Term

5.6.2.3 Safety topics of interest

Safety topics of interest for this study include infections (serious, opportunistic, fungal, and TB), IBD, and injection site reactions. Additionally, in keeping with the conduct of the adult bimekizumab program, the following topics will also be closely monitored: neutropenia, hypersensitivity (including anaphylaxis), major cardiovascular events, liver function test changes/enzyme elevations, malignancies, and SIB (see Section 5.6.2.4). Safety topics of interest are defined as events for which special monitoring, additional data collection activities, and/or enhanced signal detection activities are applied.

The TEAEs of safety topics of interest and safety topics closely monitored will be presented in a combined table. The participant incidence, number of events, and exposure adjusted rates (incidence and event rate per 100 participant years) will be reported by SOC, HLT, and PT. Summaries will be provided for the Initial Treatment Period, OLE Period, and All Periods (Initial Treatment Period + OLE Period).

The details of each safety topics of interest are provided below.

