3 OBJECTIVES AND ENDPOINTS

Objectives	Endpoints
Primary	

 To assess the PK of bimekizumab administered subcutaneously (sc) in adolescents with moderate to severe plaque PSO 	
 Bimekizumab plasma concentrations
Secondary	

 To evaluate the safety of bimekizumab in adolescents with moderate to severe plaque PSO 	
 Treatment-emergent adverse events (TEAEs) Serious TEAEs TEAEs leading to discontinuation of investigational medicinal product (IMP) TEAEs leading to withdrawal from the study Selected safety topics of interest (including infection [serious, opportunistic, fungal, and tuberculosis (TB)], inflammatory bowel disease [IBD], and injection site reactions) with onset occurring from day of first dose through 20 weeks after final dose of IMP adjusted by duration of participant exposure to IMP Change from Baseline in vital signs and physical examination findings Change from Baseline in laboratory analyses (chemistry and hematology) Growth assessment as assessed by the change in height and weight

 To evaluate the efficacy of bimekizumab in adolescents with moderate to severe plaque PSO 	
 Psoriasis Area and Severity Index (PASI) 90 response at Week 16 Investigator's Global Assessment (IGA) 0/1 response (Clear [0]/Almost Clear [1] with at least 2-category improvement from Baseline) at Week 16 PASI75 response at Week 4

Objectives	Endpoints

 To evaluate the immunogenicity of bimekizumab in adolescents with moderate to severe plaque PSO 	
 Anti-bimekizumab antibody detection prior to and following IMP administration

 To evaluate the change in quality of life in adolescents with moderate to severe plaque PSO 	
 Change from Baseline in Children's Dermatology Life Quality Index (CDLQI) response at Week 16
Other	

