5.6.1.2 Open Label Extension (OLE) Period

Duration of exposure (days):

Study participants who are enrolled into OLE Period may be allowed dose modification from the Initial Treatment Period. The duration of exposure will be calculated by aggregating distinct dosing periods with respect to each dose level.

The exposure for the i -th dosing period P_i can be calculated as follows:

- *Exposure(P_i) = Last Dose Date of P_i – 1st Dose Date of P_i + min (28, Date of Death – Last Dose Date of P_i)*

Note: If *Last Dose Date of P_i + 28* extends to a date beyond the date of first dose of the next dosing period, then this calculation reverts to:

- *Exposure(P_i) = First Dose Date of P_{i+1} – 1st Dose Date of P_i + 1*

The aggregated exposure for dose level (say A) is the sum of the exposure over all the dosing periods of dose level A:

- *Dose A Exposure = $\sum_{\text{Dose A dosing periods}} \text{Exposure}(P_i)$*

Note: If days between the last dose of P_i and the first dose of P_{i+1} is more than 28 days, then there will be a gap in between the two periods.

Time at risk (days):

For any dosing period P_i before the last dosing period,

- *Time at Risk (P_i) = min (First Dose Date of P_{i+1} , Date of Death) – 1st Dose Date of P_i + 1*

For the last dosing period P_n ,

- *Time at Risk(P_i) = Last Dose Date of P_n – 1st Dose Date of P_n + min (141, Date of Death – Last Dose Date of P_n)*

The aggregated time at risk for dose level is calculated in a similar fashion as the aggregated exposure:

- *Dose A Time at Risk = $\sum_{\text{Dose A dosing periods}} \text{Time at Risk}(P_i)$*

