5.6.2.1 General data considerations for AEs

Treatment-emergent AEs are defined as those AEs that have a start date on or following the first dose of IMP through the final dose of study treatment +20 weeks (140 days).

The rules for imputing partial start or stop dates are outlined in Section 5.14.7.5. If it is not possible (due to partial dates) to determine whether an AE is treatment-emergent then it will be assumed to be a TEAE. If the intensity of an AE is unknown, it will be considered as severe. If the relationship to study drug is missing, it will be considered as related.

Treatment-emergent AEs will be summarized as participant incidence (number and percentage of participants experiencing the AE) and AE frequencies (number of AEs including repeat events) by weight-categorized dose group for the Initial Treatment Period, OLE Period, and the combined periods. Treatment-emergent AEs will be attributed to Initial Treatment Period and OLE Period based on duration of exposure definition in Section 5.6.1. For AEs that emerged after 140 days of first dosing but still within the 140 days after last dose window, those AEs will be classified as TEAE but will be excluded from the output based on the Initial Treatment Period. However, these AEs will be included in the AE summaries for Initial Treatment Period and OLE Treatment Period combined.

For AEs that emerged > 140 days after the last dose, these AEs will only be listed in an “All Adverse Events” listing and will not be summarized.

Selected AE summaries will include the exposure-adjusted incidence rate (EAIR) and the exposure-adjusted event rate (EAER). The 95% CIs will be reported for the EAIR only.

The EAIR is the total number of participants with a specific AE divided by the total time at risk across all participants. If a participant has multiple events, the time of exposure is calculated to the first occurrence of the AE being considered with respect to the period being summarized. If a participant has no events, the total time at risk is used. The EAER is the total number of AEs including repeat occurrences in individual participants divided by the total time at risk across all participants with respect to the period being summarized. Exposure adjusted rates (EAIR and EAER) will be scaled to 100 participant-years. Participant time at risk represents the time a participant is at risk for having an AE. These definitions will be used in calculations of exposure-adjusted rates for adverse events.

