5.6.2.3.3 Injection site reactions

Injection site reactions will be evaluated in the combined table by looking under the following HLTs: “Administration site reactions NEC” and “Injection site reactions”

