5.6.2.4.1 Hypersensitivity (including anaphylaxis)

The combined table will include acute anaphylactic events (reported on the same day as when an injection was administered or 1 day after) prepared based on the MedDRA anaphylaxis algorithm (see Section 6.1.8.1). All TEAEs which code to a PT included in the Scope=Narrow search will be included in the combined table. The combined table will also summarize serious hypersensitivity events, identified using the SMQ “Hypersensitivity (SMQ)”. All serious TEAEs which code to a PT included in the Scope=Narrow search will be included in the combined table. An AE glossary table will also be produced to summarize the MedDRA coding for these events. The glossary table will include the following fields: reported term, PT, LLT, HLT, and SOC.

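### In the OLE and combined tables, rates for injection site reactions and acute anaphylaxis include up to 141 days after the last dose, when no injections are given; add a per-injection or exposure-based rate

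*SAP*

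**What the plan says.** SAP 5.6.2.3 and 5.6.2.4 put the safety topics of interest and the closely monitored topics into one table with a common set of rates: "The participant incidence, number of events, and exposure adjusted rates (incidence and event rate per 100 participant years) will be reported by SOC, HLT, and" (the list ends with preferred term). SAP 5.6.2.1 fixes the denominator: "The EAIR is the total number of participants with a specific AE divided by the total time at risk across all participants". The event rate (EAER) uses the same total. For the incidence rate (EAIR), time stops at the first event: "If a participant has multiple events, the time of exposure is calculated to the first occurrence of the AE being considered".

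Time at risk is built differently in each period:

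- **Initial Treatment Period (ITP), SAP 5.6.1.1.** A participant who continues has the days from first ITP dose to first OLE dose, plus 1. One who does not continue has at most 140 days counted from the first dose.
- **OLE, SAP 5.6.1.2.** The rule that opens "For any dosing period P_i before the last dosing period" ends such a period at the next period's first dose, plus 1 day. The last dosing period instead adds "min (141, Date of Death – Last Dose Date of P_n") to the dosing span, so only death shortens the 141 days.
- **Combined, SAP 5.6.1.3.** The two are summed for each dose level, minus 1 day.

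Duration of exposure is defined separately, as last dose minus first dose plus 28 days.

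On the two topics, SAP 5.6.2.4.1 counts "acute anaphylactic events (reported on the same day as when an injection was administered or 1 day after"). SAP 5.6.2.3.3 states: "Injection site reactions will be evaluated in the combined table by looking under the following HLTs", and sets no time window. The protocol endpoint (section 3) counts onsets up to 20 weeks after the final dose, "adjusted by duration of participant exposure to IMP".

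**The concern.** Infections or inflammatory bowel disease can begin at any time in the 20 weeks after the last dose, so time at risk is a sensible denominator for them. An acute anaphylactic event, under the SAP's own rule, cannot be counted in that stretch beyond the day after the last injection. Injection site reactions are linked to an injection in the SAP's attribution rule (5.6.2): on a switch day, adverse events generally stay with the old dose, but administration and injection site reactions, anaphylaxis and hypersensitivity go to the new dose or the dose at onset. The numerator therefore follows the injection and the denominator does not.

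Two things follow. Rates for these topics are diluted by time without injections. And because only the last dosing period carries the tail, a participant who switches dose leaves a tail-free denominator in the old dose column and brings the full tail into the new one. Switching is permitted in the OLE, either to the PS0021 dose or on crossing the weight boundary (Protocol 6.6, SAP 5.1.1.3). Injection site reactions are part of a named secondary safety endpoint; anaphylaxis is a closely monitored topic.

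**Working it through.** **Inputs.** Dosing is every 4 weeks. The ITP has 5 dosing visits (Weeks 0 to 16). The last OLE dose is at Week 120, since SAP 5.7.1.1 says none is given at Week 124. This agrees with the stated maximum study duration: 5 weeks of screening + 120 weeks from first to last dose + 20 weeks of follow-up = 145 weeks, as in the protocol synopsis. OLE dosing visits: (120 − 20)/4 + 1 = 26. The documents give no reaction rate. The EAER ratios below need only equal risk per dosing visit; the EAIR figures need an assumed level of that risk.

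**1. Initial Treatment Period.** A continuing participant has 5 visits in 141 days. Dosing-covered time is 5 × 28 = 140 days, and 140/141 = 0.993. There is no 141-day tail. Injection-free time enters only for someone who stops early and is followed to Week 20 (one dose in 140 days: 28/140 = 0.20).

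**2. On-schedule completer, EAER.**
- OLE: time at risk 700 + 141 = 841 days; covered 700 + 28 = 728 days; 728/841 = 0.866, so 13% low.
- Combined: time at risk 141 + 841 − 1 = 981 days; covered 31 × 28 = 868 days; 868/981 = 0.885, so 12% low.
- The excess is 141 − 28 = 113 days, because 28 of the 141 days are the ordinary dosing interval.
- At an assumed 2% risk per visit, the OLE rate is 22.6 instead of 26.1 per 100 participant-years.

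**3. OLE early stoppers, single participant.** Covered time over time at risk is 28/141 = 0.20 after 1 dose, 84/197 = 0.43 after 3 and 168/281 = 0.60 after 6.

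**4. EAIR, OLE completer.** Only participants without an event carry the tail. The factor is 0.87, 0.89, 0.93 and 0.97 at assumed risks of 0.5%, 2%, 5% and 10% per visit.

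**5. One participant who switches dose.** Visits per day at risk, after against before the switch:

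| Switch | Before | After | Ratio |
|---|---|---|---|
| Week 32 | 3/85 | 23/757 | 0.86 |
| Week 64 | 11/309 | 15/533 | 0.79 |
| Week 92 | 18/505 | 8/337 | 0.67 |

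With duration of exposure as denominator, each dosing period counts 28 days per dose and all three ratios are 1.00.

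**6. Pooled columns (assumed mix).** The receiving column has 20 stayers and 20 participants switching in at Week 64; the other column holds those 20 before the switch.
- OLE: (20 × 26 + 20 × 15)/(20 × 841 + 20 × 533) = 820/27,480, against 220/6,180; ratio 0.84.
- Combined: 920/30,280 against 320/8,980; ratio 0.85.

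**7. Unequal stopping without switching.** If 10% to 50% of one column stop after 3 to 6 OLE doses and the other column all complete, the ratio runs from 0.99 to 0.90. With equal retention and no switching it is 1.00.

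**The case against.** The case for leaving the plan alone has real substance.

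- **The protocol sets the 20-week window.** The endpoint counts onsets to 20 weeks after the final dose, and time at risk matches that. This stands for the other topics. Simply cutting the denominator at 28 days would also leave a late coded reaction with no person-time, since the SAP gives injection site reactions no window. That such reactions arise only near an injection is a clinical assumption, though the attribution rule supports it.
- **The consequence is modest.** All analyses are descriptive, and participant counts and event numbers sit beside the rates. With 5 participants having an event, an exact Poisson interval runs from about 0.32 to 2.3 times the estimate, far wider than a 12% to 13% shift. This stands for precision. It does not excuse a shift with a known direction.
- **Replacing the rates would depart from the protocol,** which plans selected rates per 100 patient-years with confidence intervals (9.4.1.1). This stands, so the change should be an addition.

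A reader might also infer more than the documents support:

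- *That the randomised comparison is distorted by switching.* Protocol 6.6 allows no dose modification in the ITP, and the ITP table has its own time at risk without the tail.
- *That the column rates reflect switching and dropout instead of reaction risk.* They reflect both, and the single-participant ratios are not column rates. The documents give no switching or discontinuation frequencies.
- *That the tail explains why anaphylaxis is countable on only 62 of 981 days (31 visits × 2 days, 6%).* Without the tail it is 62/868, or 7%. Nearly all the remaining days are ordinary time between doses.

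**Conclusion.** The point holds for the OLE and combined tables and for two topics only: injection site reactions and acute anaphylactic events. For an on-schedule completer the EAER is 12% to 13% low, and the EAIR less so. Differences between dose columns are conditional: they need dose switching or unequal early stopping. In the illustrations they reach a ratio of 0.84 to 0.85 for pooled columns, with the dose received last appearing better tolerated.

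These sizes assume on-schedule dosing and equal risk per dosing visit; the pooled figures also assume the 20-and-20 mix. They are per dosing visit. If dose levels differ in injections per visit (the presentation is redacted, so this is open), per-injection figures will differ from them.

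There is also a loose end in notation. In SAP 6.1.6.2 the EAIR formula uses T_Risk, while its legend and the confidence limits use T_Exp. One might infer that the rate and its interval will have different denominators. The text of 5.6.2.1 points to time at risk for the rate, so this may be notation only, but it should be settled. SAP 6.2 does not list the choice of time at risk among the changes from the protocol. This is a cheap improvement to a descriptive safety summary, not a threat to the primary pharmacokinetic objective.

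**What to change.** 1. Keep the planned rates per 100 participant-years for every topic.
2. For injection site reactions and acute anaphylactic events, in the OLE and combined tables, add one of:
   - events per 100 injections, using the completed injections already counted for compliance (SAP 6.1.10), with the number of injections shown for each column; or
   - a rate on the SAP's own duration of exposure (last dose + 28 days), with any event after that window listed separately.
3. Footnote that these rows use a different denominator.
4. Reconcile T_Risk and T_Exp in SAP 6.1.6.2 with each other and with the endpoint wording "adjusted by duration of participant exposure to IMP".

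The per-injection version is preferable if dose levels differ in injections per visit, because it adjusts for that as well as for the tail. The cost is SAP wording, one additional row per topic and a footnote; no new data are needed. The drawback is that these two topics will not share the denominator of the others in those rows.

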5.6.2.3.1 Infections (serious, opportunistic, fungal and TB)

- Serious infections: The combined table will include serious infections identified based on MedDRA classification (SOC “Infections and infestations”) using the “Any SAE” table.
- Fungal infections: The combined table will include all TEAEs (serious and non-serious) which code into the High Level Group Term “Fungal infections disorders”.
- Opportunistic infections (including TB): The combined table will include all TEAEs identified using the SMQ “Opportunistic infections (SMQ)”. All TEAEs which code to a PT included in the Scope = Narrow search will be included in this table.

- TB: TB will be analyzed as part of opportunistic infections. Summary of the number and percentage of participants with negative, positive, and indeterminate interferon gamma release assay (IGRA) results at each visit will be presented. In addition, incidence of TB related TEAEs will be summarized (active TB, latent TB, and false positive TB testing). A by-participant listing of the “Evaluation of signs and symptoms of tuberculosis” questionnaire data, IGRA results, and chest x-ray results will be provided. A by-participant listing of “All Treatment-Emergent Adverse Events Related to TB including latent TB and IGRA tests” will be provided.

5.6.2.3.2 IBD

An external IBD adjudication committee will evaluate potential IBD events and will classify each one as follows:

- Event Type Code 1: Possible IBD – Crohn’s Disease
- Event Type Code 2: Probable IBD – Crohn’s Disease
- Event Type Code 3: Definite IBD – Crohn’s Disease
- Event Type Code 4: Possible IBD – Ulcerative Colitis
- Event Type Code 5: Probable IBD – Ulcerative Colitis
- Event Type Code 6: Definite IBD – Ulcerative Colitis
- Event Type Code 7: Possible IBD – Unclassified
- Event Type Code 8: Probable IBD – Unclassified
- Event Type Code 9: Definite IBD – Unclassified
- Event Type Code 10: Symptoms not consistent with IBD
- Event Type Code 11: Possible Inflammatory Bowel Disease – Microscopic Colitis
- Event Type Code 12: Probable Inflammatory Bowel Disease – Microscopic Colitis
- Event Type Code 13: Definite Inflammatory Bowel Disease – Microscopic Colitis
- Event Type Code 14: Possible Inflammatory Bowel Disease – no further differentiation possible
- Event Type Code 15: Probable Inflammatory Bowel Disease – no further differentiation possible
- Event Type Code 16: Definite Inflammatory Bowel Disease – no further differentiation possible
- Event Type Code 99: Not enough information to adjudicate

The combined safety topics of interest and safety topics closely monitored table will summarize events determined by the adjudication committee as definite IBD (event type codes 3, 6, 9, 13, and 16) and probable IBD (event type codes 2, 5, 8, 12, and 15).

A separate table will present the incidence and event rate of adjudicated gastrointestinal events by type for the combined ITP and OLE Period. For each gastrointestinal event type (17 total), the

individual PTs which fall within each event type will be summarized. It will include events determined by the adjudication committee as definite IBD, probable IBD, and possible IBD. It will also include events determined as Symptoms not consistent with IBD (event type code 10) and Not enough information to adjudicated (event type code 99).

A listing of all events identified for potential review by the IBD adjudication committee will be produced. This listing will indicate whether each event was escalated to the committee for formal review/adjudication.

A separate listing will present the adjudicated IBD events by type. For each IBD event type (event type codes 1 through 16 and 99; 17 total), the individual PTs which fall within each event type will be listed.

A third listing will present the individual diagnostic criteria met for each adjudicated IBD event.

